### Study Sponsor(s)

Zimmer Biomet

# Clinical Research Protocol

## STUDY SUMMARY

TITLE	Prospective Multi Center Randomized Controlled Trial to evaluate G7 Acetabular System with CoC articulation compared to Exceed ABT Acetabular System with CoC articulation in Total Hip Arthroplasty
DESIGN	Prospective Randomized Controlled Trial
PURPOSE	Evaluate the safety and effectiveness of patients who received G7 Acetabular system in conjunction with Ceramic on Ceramic articulation and Taperloc Complete Microplasty stem compared to patients who received the Exceed ABT Acetabular system with the same combination
OUTCOME MEASURES	160 patients (80 per group)
POPULATION	
ELIGIBILITY	Approved Indications for Use for G7 Acetabular System, Exceed ABT Acetabular System and Taperloc Complete Microplasty stem in Total Hip Arthroplasty
DURATION	All patients will be followed at 6 months, 1, and 2 years postoperatively. Assuming the enrolment will be completed in one year, the total duration of the study is 3 years.

# Clinical Research Protocol

## 1. INTRODUCTION

### 1.1. BACKGROUND

The Biomet G7™ Acetabular System has been designed to provide more options to surgeons for treatment of patients needing total hip arthroplasty, while concurrently simplifying the surgical process with well-designed, modular components and corresponding instruments. The G7™ Acetabular System includes three liner types; ArComXL highly-crosslinked or E-1 Vitamin E-infused polyethylene and a Biolox Delta (Ceramtec, Plochingen, Germany) ceramic liner.

The Exceed ABT Acetabular System has been designed for cementless fixation and consists of an acetabular shell and an acetabular insert. The acetabular insert/bearing includes a tapered outer geometry that matches the inner geometry of the acetabular shell and an inner hemispherical geometry to suit the varying modular head diameters. Inserts/bearings are inserted into the acetabular shell intra-operatively and are available in varying sizes to match the acetabular shell diameters. The insert/bearings are available in Biolox Delta ceramic (CeramTec AG).

G7 is a new acetabular system and to support its launch and ensure it continues to perform as intended, clinical evidence is required to be collected. There is also a need to collect clinical data on Exceed ABT to continue supporting marketing.

### 1.2. DEVICE DESIGN AND DESCRIPTION

#### **The Biomet G7™ Acetabular System**

The Biomet G7 Acetabular System is a modular acetabular system, offering two types of acetabular shells. The shells are available in either a solid shell design, with an apical plug, or a limited hole with an apical plug and optional screw holes. Components are available in numerous designs and sizes intended for both primary and/or revision applications.

All patients that consent to the study will be operated by either posterior-lateral or antero-lateral incision approach which are standard incision approaches for treatment of patients needing total hip arthroplasty.

#### Cup materials

Acetabular Shells are made of porous coated (PPS) titanium alloy. Screw hole and apical hole plugs are also made of titanium alloy. It contains options to use acetabular screws.

The acetabular shell is designed to be used with multiple bearings.

In the current study, the ceramic on ceramic articulation will be used.

#### Ceramic materials

Ceramic Acetabular Liners are made of zirconia-platelet toughened alumina (ZPTA)

#### **The Biomet Exceed ABT Acetabular System**

In the current study, the ceramic on ceramic articulation will be used.

#### Cup materials

Acetabular Shell: Titanium alloy Biolox® delta Ceramic Inserts Toughened alumina

Acetabular Screws: Titanium alloy

PPS porous plasma spray coating

#### **Taperloc Complete Microplasty stem.**

Biomet® Taperloc™ Complete stems are intended for uncemented biological fixation. They are offered in several sizes in both a standard and high offset design. The Taperloc™ Complete hip stems can be used for total hip arthroplasty.

# Clinical Research Protocol

Stem materials:

Femoral Stems	Titanium Alloy
Porous Coating	Titanium Alloy

All the sites will use the Taperloc Complete Microplasty stem designed for ease of insertion with an posterior hip approach

- Stem length reduced to 35 mm from standard length stem
- Bone conserving stem option
- High offset options will also be available for the study

## 1.3. RATIONALE FOR CURRENT STUDY

To insure G7 Acetabular system and Exceed ABT Acetabular system perform as they are intended, clinical evidence is required to be collected.

## 1.4. PURPOSES

The purpose of the study is to evaluate the safety and effectiveness of patients who received G7 Acetabular system in conjunction with Ceramic on Ceramic articulation and Taperloc Complete Microplasty stem in primary total hip arthroplasty compared to patients who received the Exceed ABT Acetabular system with the same combination.

# 2. STUDY DESIGN

## 2.1. OVERALL DESIGN

This study will be a multi-center randomized controlled study. Eligible patients will be randomly assigned to receive a combination of G7 Acetabular system with CoC articulation and Taperloc Complete Microplasty stem or Exceed ABT Acetabular system with CoC articulation and Taperloc Complete Microplasty stem. Patient demographics, preoperative clinical outcomes, operative information, postoperative clinical outcome, radiographic assessment, incidence of squeaking, incidence of dislocation, implant survivorship and adverse events will be collected prospectively.

## 2.2. NUMBER OF SITES AND SUBJECTS/PROCEDURES

This is a multi-center study to be conducted in Korea at a maximum of 4 sites

## 2.3. EFFICACY AND/OR SAFETY HYPOTHESES

This study is designed to evaluate any difference in terms of patient reported clinical outcome (i.e. OHS, HHS) postoperatively in patients who received one of the abovementioned combinations of total hip systems.

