# Clinical Research Protocol

## 6. STATISTICAL ANALYSIS PLAN

### 6.1 SAMPLE SIZE CALCULATION

This is a multi-center, randomized controlled study to compare G7 Acetabular System /CoC articulation/Taperloc Complete Microplasty stem with Exceed ABT Acetabular System /CoC articulation/Taperloc Complete Microplasty stem. The primary endpoint is Harris Hip Score at 1 year postop. Study sample size is determined assuming the use of an independent, two-sided, two-sample pooled t-test for differences in mean Harris Hip Score.

Assumptions:

$\alpha = 0.05$	Probability of Type I Error
$\beta = 0.20$	Probability of Type II Error
$sd = 12$	Estimated standard deviation of the differences based on current Exceed ABT CoC study in Korea

Based on the assumptions above, a mean difference in Harris Hip Score of 5.8 points between groups can be detected with 68 cases in each group. If 15% dropout/lost to follow-up is assumed this will give n=80 in each group.

A total of 160 cases will be enrolled in the study.

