### 6.2 HANDLING OF MISSING AND INCOMPLETE DATA

Attempt will be made to ensure that patients come back for scheduled follow-up evaluations. In case of missing data, for clinical outcome scores, Last Observation Carried Forward will be used to impute the missing data. For survivorship analysis, the data including implant in situ collected in the next follow-up will be used to calculate survivorship

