# Clinical Research Protocol

## Primary and Secondary Endpoint Analysis

Analysis for primary and secondary endpoints will use patient population which consists of those cases with complete data for one or more of the primary and secondary endpoints. Analysis is based on intention to treat principle.

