# Clinical Research Protocol

## 8. DATA REPORTING

### 8.1 INTERIM REPORT

An interim report will be provided after each follow-up period.

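### Does the plan need a non-inferiority threshold or reading rule in case the 1-year Harris Hip Score comparison is not significant?

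*Combined protocol and SAP*

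**What the plan says.** The background (1.1) wants clinical evidence on G7 "to support its launch and ensure it continues to perform as intended", and also wants data on Exceed ABT. The rationale (1.3) names both cups: "To insure G7 Acetabular system and Exceed ABT Acetabular system perform as they are intended". Neither section compares them. The comparison enters in 1.4, where safety and effectiveness of G7 are to be evaluated "in primary total hip arthroplasty compared to patients who received the Exceed ABT Acetabular system with the same combination". That wording is neutral about the expected result.

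The hypothesis (2.3) is two-directional: "This study is designed to evaluate any difference in terms of patient reported clinical outcome (i.e. OHS, HHS) postoperatively". Section 6.1 assumes a two-sided pooled t-test with alpha 0.05, beta 0.20 and SD 12, and states that "a mean difference in Harris Hip Score of 5.8 points between groups can be detected with 68 cases in each group", which becomes 80 per group after 15% dropout.

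Section 6.3 lists the endpoints again. Its last part defines the analysis population as "those cases with complete data for one or more of the primary and secondary endpoints" and invokes intention to treat. It names no effect estimate, interval, margin or rule for reading the primary result. Section 6.2 adds that "for clinical outcome scores, Last Observation Carried Forward will be used to impute the missing data". Section 8.1 adds that "An interim report will be provided after each follow-up period".

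**The concern.** A difference test can show that two cups differ. When it does not, the p-value alone does not say how large a G7 deficit remains compatible with the data. Someone who reads 1.1, 1.3 and 1.4 together may conclude that the real aim is reassurance about G7 against Exceed ABT. On that reading the plan lacks the one thing that could deliver it on the primary endpoint: a stated loss to be ruled out.

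What would be at stake is a non-significant 1-year HHS being presented as comparability when the interval still allows a material deficit. Because reports are issued after each follow-up period, the interpretation could also be settled after data had been seen. The natural remedy would be a justified threshold, a decision rule based on the lower confidence limit, and a supporting sensitivity analysis.

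**Working it through.** **Inputs (6.1).** Two-sided alpha 0.05, power 0.80, SD 12, difference 5.8, 68 evaluable per group, 15% dropout. Section 6.1 labels the SD as that of the differences. It is used here as the between-patient SD, because that use reproduces the stated size.

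**The plan's own figure.** n per group = 2 × (1.960 + 0.842)² × 12² / 5.8² = 67.2, rounded up to 68. Then 68 / 0.85 = 80, or 160 in total. The exact t-test power at 68 is 79.9%. A one-sided test would need only 53, so the size belongs to the two-sided difference question of 2.3.

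**Precision.** SE = 12 × √(2/68) = 2.058. The 95% half-width is 1.978 × 2.058 = 4.07. If the analysed number approaches 80 per group, as it may after imputation, SE = 12 × √(2/80) = 1.897 and the half-width is 3.75, provided the SD stays at 12.

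**What a non-significant result can hide (68 per group, G7 minus Exceed ABT).**
- Worst case: an observed deficit just short of 4.07 has a lower limit of −2 × 4.07 = −8.14. With a true difference of 0, a non-significant result with a lower limit below −8 occurs in about 0.8% of trials. With a true 4-point deficit it occurs in about 5%.
- Typical case at a true difference of 0: the lower limit is about −4.1, which excludes a 5.8-point deficit.
- Share of non-significant results that fail to exclude 5.8, at a true difference of 0: the lower limit lies at or below −5.8 with probability 1 − 0.799 = 0.201. Of this, 0.025 are significant deficits. So (0.201 − 0.025) / 0.95 = 0.185.
- Probability of p>0.05 if G7 is truly worse by 3, 4, 5 or 5.8 points: 70%, 51%, 33% and 20%. This is the ordinary type II error of a trial sized at 80% power for 5.8.

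**What a no-worse rule would cost.** The rule requires the lower 95% limit to lie above minus the threshold. The documents give no threshold, so a range is assumed. Power is at a true difference of 0, and enrolled = evaluable / 0.85.

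| Threshold | Power at 68 per group | Power at 80 per group | Evaluable per group for 80% | Enrolled per group |
|---|---|---|---|---|
| 3 | 30% | 35% | 253 | 298 |
| 4 | 49% | 55% | 143 | 169 |
| 5 | 67% | 75% | 92 | 109 |
| 5.8 | 80% | 86% | about 68 | about 80 |

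The sizes for 3, 4 and 5 points are exact noncentral-t values; the normal approximation gives one fewer evaluable per group (252, 142, 91). At 5.8 and 68 per group, a true 1-point G7 deficit reduces the rule's power to 64%.

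**The case for a change.** The strongest case for a change runs as follows. Section 6.3 promises analyses and then only lists endpoints, so the primary comparison has no prespecified output beyond a test borrowed from the sample-size section. A true 4-point deficit would pass as non-significant about half the time. Nothing in the plan stops that result from being read as reassurance, and reports are issued along the way. Naming the interval and adding a sentence on p>0.05 would cost no patients and no alpha.

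Part of this stands. The text is silent on the interval and on how a null result is read, and p>0.05 alone would not show comparability. If the sponsor wished to claim that G7 is no worse, a justified threshold would have to be fixed beforehand. The 5.8 points could not serve by default, because 6.1 presents it as a detectable difference and not as an acceptable loss.

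The rest does not carry. The rationale is not comparative and the comparative purpose is neutral; a comparability aim appears only when the two are joined. No section says that non-significance will count as support, so the harm needs a null result and then a misreading that the plan does not announce. Evidence on performing as intended also comes from radiographs, squeaking, dislocation and survivorship (2.4) and from adverse events (section 5), not from 1-year HHS alone. That the carry-forward rule and the analysis set pull the arms together is possible but not shown; it is a separate question about missing data.

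**Conclusion.** No change to the plan is needed. The hypothesis, the two-sided test and the sample size answer the same question, and the stated 68 and 80 per group reproduce. Followed as written, the plan gives a valid test of a difference. What is missing is reporting detail that a competent analyst supplies as a matter of course: the G7 minus Exceed ABT difference with its 95% interval, about ±4.07 points at 68 per group or ±3.75 at 80. That interval shows directly which deficits remain possible, including in the roughly 18.5% of non-significant results (true difference 0, 68 per group) that would not exclude 5.8 points.

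The larger remedy would turn a difference trial into a non-inferiority trial. The documents offer no margin for it. At thresholds of 3 to 5 points it would have 30% to 67% power at the planned 68 evaluable per group, or would need 109 to 298 enrolled per group. Whether to add that aim is the sponsor's choice; leaving it out is not an error.

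The conclusion assumes a between-patient SD of 12, equal groups and approximate normality of the mean difference. It would change if the sponsor intended to claim that G7 is no worse than Exceed ABT on the strength of 1-year HHS. The current text makes no such claim.

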## 2.4. PRIMARY AND SECONDARY ENDPOINTS

Primary endpoint is Harris Hip Score (HHS) at 1 year follow-up.

Secondary endpoints include

- Harris Hip Score at 2 years postop
- Oxford Hip Score at 6 months, 1 and 2 years postop
- Radiographic Assessment at Immediate post-op, 6 months, 1 and 2 years postop
- Incidence of squeaking at different follow-up visits
- Dislocation rate at different follow-up visits
- Survivorship

# Clinical Research Protocol

## 2.5. ASSESSMENT PROCEDURE

### 2.5.1. ASSESSMENT PARAMETERS AND METHODS

#### Medical History and Demographic Data

Demographic information will be collected which will include but is not limited to gender, age at surgery, height, weight, primary diagnosis & medical history

#### Clinical Assessments

Clinical assessments will include functional scores, radiographic analysis.

An operative record will be completed upon the surgery. The operative record will include but are not restricted to date of surgery, surgical approach, implant components (part number).

#### Radiographic Assessments

Standardized antero-posterior pelvis radiographs and true lateral hip radiographs will be taken at each follow-up period. Femoral and acetabular implant position will be measured and the presence of signs of loosening will be analyzed. Radiographs will also be assessed for all time points using Gruen zone analysis of the femoral component and Charnley-DeLee zone analysis of the acetabular system

### 2.5.2. ASSESSMENT TIMELINES/SCHEDULE

Clinical and Radiographic Exams						
Data Collection item	Pre-operative	Intra-operative	Immediate Post-operative	6 Months	1 Year	2 years
Demographic and Medical History	X					
Operative Record		X				
Clinical Evaluation – OHS, HHS	X			X	X	X
Radiographic assessment			X	X	X	X
Squeaking, Dislocation			X	X	X	X
Adverse events including revisions			As required			

### 2.5.3. ALLOWED WINDOW OF EACH SCHEDULE

# Clinical Research Protocol

Allowed Window of Each Prospective Visit Schedule:

- 6 months (+/- 2 weeks)
- 1 year (+/- 2 months)
- 2 years (+/- 3 months)

Each follow-up visit time point will be determined based on the date of surgery.

## 2.6. DURATION OF THE STUDY

All cases will be followed up to 2 years. It is expected that the enrollment will be completed in 1 year; the total duration of the study is 3 years.

## 3. SELECTION AND WITHDRAWAL OF SUBJECTS

All subjects, regardless of sex, race, or geographic location, must fit into the scope of the Inclusion/Exclusion criteria to be eligible for the study. If required per applicable regulations, all participants must sign an Informed Consent to be enrolled into the study.

### 3.1 INCLUSION CRITERIA

Patients will be included in this study to receive G7 Acetabular System, Exceed ABT Acetabular System, Ceramic on Ceramic articulation and Taperloc Complete Microplasty stem per the approved indications for use:

1. Non-inflammatory degenerative joint disease, including osteoarthritis and avascular necrosis.
2. Rheumatoid arthritis.
3. Correction of functional deformity.
4. Treatment of non-union, femoral neck fracture, and trochanteric fractures of the proximal femur with head involvement, unmanageable by other techniques.
5. Revision of previously failed total hip arthroplasty.
6. age over 20 years old

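### Primary diagnosis is collected across a wide mix of indications, but no stratification or adjustment for it is specified; prespecifying it would be a cheap gain in precision for 1-year HHS, not a bias correction.

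*Combined protocol and SAP*

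**What the plan says.** - **Eligibility (3.1).** Listed indications are non-inflammatory degenerative disease (osteoarthritis and avascular necrosis named), rheumatoid arthritis, functional deformity, "Treatment of non-union, femoral neck fracture, and trochanteric fractures of the proximal femur with head involvement, unmanageable by other techniques", and revision of a previously failed total hip arthroplasty. Section 1.4 describes the purpose as a comparison in primary total hip arthroplasty.
- **Baseline data (2.5.1).** The form records "gender, age at surgery, height, weight, primary diagnosis & medical history". The schedule in 2.5.2 also places "Clinical Evaluation – OHS, HHS" before surgery.
- **Randomisation (under 6.1).** Allocation is 1:1 in blocks of 4. No stratification factor is named.
- **Sample size (6.1).** The size is set "assuming the use of an independent, two-sided, two-sample pooled t-test for differences in mean Harris Hip Score". The SD of 12 is described as "Estimated standard deviation of the differences based on current Exceed ABT CoC study in Korea".
- **Analysis (6.2 and 6.3).** These sections give the endpoints, last observation carried forward for missing scores, the analysis population and the intention-to-treat principle. They name no model, covariate or subgroup.

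**The concern.** The eligible indications differ enough that HHS at 1 year may well differ between them. If it does, an unadjusted comparison leaves that variation in the error term, although the trial already holds the variable that would remove it. Stratifying on diagnosis, or fitting it as a covariate, would recover some of that precision without new data. Because 6.3 names no model, the choice of covariates is also still open. Section 8.1 provides for an interim report after each follow-up period, so covariates not fixed in advance could end up being chosen with outcome data in view.

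**Working it through.** **Inputs from 6.1:** two-sided alpha 0.05, power 0.80, SD 12, difference 5.8 points, 68 evaluable per group, 15% dropout.

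**Assumed, because the documents do not give them:** the share p of patients in lower-scoring diagnoses, and the gap g in 1-year HHS between them and the rest.

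**Step 1. Reproduce the plan's figures.** n = 2(1.960 + 0.842)² × 12² / 5.8² = 67.2, so 68 per group. 68 / 0.85 = 80. Both match 6.1. Exact noncentral-t power at 68 per group is 79.9%.

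**Step 2. Cost of the diagnosis terms.** With N = 136 and k diagnosis terms, the variance of the treatment difference rises on average by the factor 1 + k/(N − k − 3), and the error degrees of freedom fall from 134 to 134 − k.
- k = 2 (three groups): 1 + 2/131 = 1.015.
- k = 3 (four groups): 1 + 3/130 = 1.023.

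If diagnosis explains nothing, power falls from 79.9% to 79.3% (k = 2) or 79.0% (k = 3), a loss of 0.6 or 0.9 points.

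**Step 3. Gain under assumed mixes.** Variation between diagnoses contributes p(1 − p)g² to the variance. The SD of 12 can be read in two ways:
- A: 12 is the SD within a diagnosis, so the total SD is √(144 + p(1 − p)g²).
- B: 12 already includes the mix, so the residual SD after adjustment is √(144 − p(1 − p)g²).

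| p, g | Reading | Total SD | Residual SD | Unadjusted power | Adjusted, k = 2 | Adjusted, k = 3 |
|---|---|---|---|---|---|---|
| 10%, 5 | A | 12.09 | 12 | 79.3% | 79.3% | 79.0% |
| 10%, 5 | B | 12 | 11.91 | 79.9% | 79.9% | 79.6% |
| 10%, 8 | A | 12.24 | 12 | 78.3% | 79.3% | 79.0% |
| 10%, 8 | B | 12 | 11.76 | 79.9% | 80.9% | 80.6% |
| 15%, 12 | A | 12.74 | 12 | 75.0% | 79.3% | 79.0% |
| 15%, 12 | B | 12 | 11.21 | 79.9% | 84.4% | 84.2% |

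The net change is about 0 to 1 point in the two weaker mixes (a loss of 0.3 in the weakest one with three terms). It is 4.0 to 4.5 points in the 15%, 12-point mix.

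**Step 4. Chance imbalance.** At p = 15%, the 95% limit for the difference in share between arms is 1.96 × √(2 × 0.15 × 0.85 / 68) = 12.0 percentage points. With a 12-point gap that moves the HHS difference by 0.120 × 12 = 1.44 points. The 95% margin of the unadjusted comparison at SD 12 is 1.96 × 12 × √(2/68) = 4.0 points, or 4.3 at SD 12.74. Those margins already reflect whatever between-diagnosis variation is in the SD.

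**The case against.** **A reader might infer that the trial is underpowered.** Under reading A, power is 75.0% in the 15%, 12-point mix, and 70.6% if 20% of patients score 15 points lower (SD √(144 + 36) = 13.42). The documents do not support this. They do not say that the SD of 12 comes from a single-diagnosis sample. Its source is a Korean study of the same comparator cup and bearing, and if that study had a similar mix the stated power holds. Nor do they point to a large fracture share: fractures qualify only when other techniques cannot manage them, and 3.2 lists osteoporosis and marked bone loss among the relative contraindications.

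**A reader might infer that a chance excess of fracture patients in one arm could pass for a cup effect.** Randomisation keeps the unadjusted test valid, and its standard error already covers such imbalance. There is no false-positive risk beyond the nominal 5%.

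**A reader might infer that the plan has chosen to ignore diagnosis.** The t-test appears only as a sample-size assumption. The exact statement is that no adjustment is specified. The wider gap is the missing primary model, in which diagnosis is one candidate covariate beside pre-operative score and site.

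**A reader might want a separate pre-operative slope for fracture patients,** on the ground that their score is taken after the injury. The documents do not say when or how it is scored in those patients. At 15% of 136 the slope would rest on about 20 patients.

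All four objections limit the size and the wording of the point. What remains is that a baseline variable already on the form has no stated role in the design or the analysis, and that giving it one costs almost nothing.

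**Conclusion.** The point holds as a modest, inexpensive improvement in precision. The unadjusted comparison is valid and meets its stated power of about 80% if SD 12 reflects a similar case mix. Whether adjustment helps depends on how common the lower-scoring diagnoses are and how far apart the diagnoses lie at 1 year, and neither is documented. Over the mixes tabulated, the balance is favourable: at best a gain of 4 to 5 points of power, at worst a loss of under 1 point. These figures assume 68 evaluable per group, one lower-scoring subset, a common SD within diagnoses, and two or three diagnosis terms. They do not include any gain from pre-operative score.

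**What to change.** In 6.3, prespecify a linear model for 1-year HHS with treatment, primary diagnosis in a few groups fixed in advance, and pre-operative HHS. Use the same form for HHS and the Oxford Hip Score at the other visits, with the matching pre-operative score. State the rule for pooling rare groups, for example a minimum count applied without sight of outcomes. Keep the unadjusted comparison as supportive. Use one common pre-operative slope.

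The groups must cover every indication that can be enrolled. Before they are set, the revision criterion in 3.1 and the primary-arthroplasty purpose in 1.4 must be reconciled; which of them should stand is for the sponsor and investigators to decide.

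The cost is a few sentences in 6.3, two or three of the 134 error degrees of freedom for the diagnosis terms (one more for pre-operative score), and under 1 point of power from the diagnosis terms if diagnosis is not prognostic. No new data, visits or patients are needed.

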#### Randomization

In this study, patients will be randomized to G7 Acetabular System with CoC articulation and Taperloc Complete Microplasty stem or Exceed ABT Acetabular System with CoC articulation and Taperloc Complete Microplasty stem in 1:1 randomization scheme. The randomization will occur via a random number generator (manual or computer) by Sponsor using block randomization procedure (block size of 4). The doctor or other health care professional does not choose the participants for each group. For patients satisfying inclusion criteria, randomization will occur by retrieving the next randomly generated group assignment. Sites will control randomization assignment.

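### Section 1.4 states the purpose as primary total hip arthroplasty, but inclusion criterion 5 makes revision eligible and the Study Summary sets no primary limit; the three need reconciling before analysis

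*Combined protocol and SAP*

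**What the plan says.** Three places in the combined protocol and SAP describe who the trial is about.

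- **Section 1.4 (Purposes)** limits the setting to primary surgery: "Taperloc Complete Microplasty stem in primary total hip arthroplasty".
- **Section 3.1 (Inclusion Criteria)**, item 5, lists "Revision of previously failed total hip arthroplasty". The list is introduced as the approved indications, but it is also the study's own list of patients to be included.
- **Study Summary**, eligibility row: "Approved Indications for Use for G7 Acetabular System, Exceed ABT Acetabular System and Taperloc Complete Microplasty stem in Total Hip Arthroplasty". The purpose row of the same table repeats the aim of Section 1.4 without the word primary.

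Two further places give the criteria their force. Section 3 says that all subjects "must fit into the scope of the Inclusion/Exclusion criteria to be eligible for the study". The Randomization text under Section 6.1 says: "For patients satisfying inclusion criteria, randomization will occur by retrieving the next randomly generated group assignment".

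The exclusion list in Section 3.2 does not name revision or previous arthroplasty. Randomization is 1:1 in blocks of 4, with no stratification by surgery type. Sections 6.2 and 6.3 and the endpoint analysis text name no covariate or subgroup for it. The analysis is stated to follow intention to treat.

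**The concern.** A hip operation is either a primary replacement or a revision of an earlier one. A purpose confined to the first and an entry criterion admitting the second cannot both define the population, and nothing in the documents says which governs the interpretation of the results.

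What is at stake is what the final report can claim. If revisions are enrolled, the pooled HHS, dislocation and survivorship results describe a mixed population, while Section 1.4 presents them as results for primary arthroplasty. With up to four sites, one site could enrol by the criteria and another by the purpose statement. Leaving the choice until the data are in would be worse, because dropping randomised revision patients at that stage would conflict with the intention-to-treat statement.

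**Working it through.** **1. The passages side by side.**

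| Place | Population | Role in the plan |
|---|---|---|
| Section 1.4 | Primary arthroplasty | Statement of purpose |
| Study Summary | Approved indications, no primary limit | Summary of eligibility |
| Section 3.1, item 5 | Revision eligible | Inclusion criterion |
| Section 3 and Randomization | Whoever meets the criteria | Decides entry and allocation |
| Section 3.2 | Revision not excluded | Exclusion criteria |

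A revision patient who meets the remaining criteria is randomised as the plan stands. Only Section 1.4 uses primary as a limit on the population. Section 1.2 mentions both primary and revision use, but there it describes the product range.

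**2. The plan's own sample size.** Inputs from Section 6.1: two-sided alpha 0.05, power 80%, SD 12, difference 5.8 points.

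- Normal formula: n = 2 × (1.960 + 0.842)² × 12² / 5.8² = 67.2, rounded up to 68 per group.
- Dropout: 68 / (1 − 0.15) = 80 per group, 160 in total.
- Noncentral-t power at 68 per group: 79.9%.

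The stated figures reproduce, so the inconsistency is not an error in N.

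**3. Illustration of size.** The documents give no revision share (w), no HHS gap between revision and primary cases (m), and no statement of whether the study behind SD 12 included revisions. All three are assumptions here, together with equal SD within each surgery type.

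*If SD 12 applies to primaries only:* pooled SD = √(144 + w(1 − w)m²), and each arm's expected mean falls by w × m.

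| w | m | Pooled SD | Power, 68 per group | Fall in each arm's mean |
|---|---|---|---|---|
| 0 | – | 12.00 | 79.9% | 0 |
| 2% | 5 | 12.02 | 79.8% | 0.1 |
| 2% | 10 | 12.08 | 79.4% | 0.2 |
| 5% | 5 | 12.05 | 79.6% | 0.25 |
| 5% | 10 | 12.20 | 78.6% | 0.5 |
| 20% | 15 | 13.42 | 70.6% | 3.0 |

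Worked line: w = 0.05, m = 10 gives 0.05 × 0.95 × 100 = 4.75, and √148.75 = 12.20.

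*If SD 12 already describes a mixture:* pooled power stays at 79.9%.

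**4. Effect of adjusting for surgery type.** The calculation uses 68 per group, one covariate, 133 degrees of freedom and variance inflation 1 + 1/134.

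- If SD 12 applies to primaries: 79.6%, whatever the share and gap.
- If SD 12 is a mixture, within-type SD = √(144 − w(1 − w)m²). At w = 20% this is 11.83, 11.31 and 10.39 for gaps of 5, 10 and 15 points, with power 80.7%, 84.1% and 89.6%.

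Adjustment therefore holds power at about 80% or raises it, with no added enrolment.

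**The case against.** The strongest reply is that the conflict turns on one word in a sentence that enrols nobody. The Study Summary, the design section and the endpoints carry no primary limit. The criteria are decisive, so a site can tell whom it may enrol, and Section 1.4 may simply contain a slip. That is plausible, and it means that the Study Summary does not contradict criterion 5. But the documents do not call it a slip, and accepting that reading only settles which text to correct.

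It can also be said that few revisions would enter. Every patient is to receive both a study cup and the Microplasty stem ("Eligible patients will be randomly assigned to receive a combination of G7 Acetabular system with CoC articulation and Taperloc Complete Microplasty stem", with the comparator arm getting the same stem), and Section 1.2 describes that stem as a "Bone conserving stem option". Section 3.2 lists marked bone loss as a relative contraindication, and Section 10.3 excludes anyone meeting an exclusion criterion. These points make a low share believable, and 20% looks high. They do not bar revision as such, since not every revision need involve marked bone loss.

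The objection that the power figures rest on assumptions stands in full. The 70.6% needs the share, the gap and the reading of SD 12 all at their least favourable, so it cannot carry the point.

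A reader might infer more: that the comparison between arms is biased, or that 160 patients are too few. The documents support neither. Allocation is random at 1:1, so revisions are expected equally in both arms, and the sample size reproduces.

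**Conclusion.** The point holds as a mismatch between the stated question and the eligible population. That much rests on the text alone: Section 1.4 says primary, criterion 5 says revision is eligible, the criteria govern entry, and nothing reconciles them.

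Its practical size is unknown. The documents report neither a revision share nor a score gap, and the share may be zero. On the assumed 2 to 5% revisions and a 5 to 10 point gap, each arm's expected mean HHS lies 0.1 to 0.5 points below the primary-only mean, equally in both arms. Power is then 78.6 to 79.8% if SD 12 applies to primaries, and unchanged at 79.9% if SD 12 already includes revisions. No dislocation or survivorship rates are given, so the effect on those endpoints is not quantified. The correction is worth making because it is cheap and must precede analysis, not because a large loss has been shown.

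**What to change.** Before analysis, bring the Study Summary, Section 1.4 and Section 3.1 into agreement in one of two ways. The documents do not settle which was intended, so the choice is the sponsor's.

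1. **If the question is primary arthroplasty:** remove criterion 5 and add the primary limit to the Study Summary, which would otherwise still admit every approved indication. Keep any revision patient already randomised in the intention-to-treat analysis. The cost is a smaller recruitment pool, by an amount that the documents do not allow to be estimated, against a planned one-year enrolment.
2. **If revisions are meant to be eligible:** correct Section 1.4 to say so, record primary or revision status as a baseline item, and include it as a covariate in the HHS analysis. Section 2.5.1 already collects "gender, age at surgery, height, weight, primary diagnosis & medical history", from which the status may be derivable. The cost is one data item at most and one covariate. A descriptive table of the primary cases is optional.

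Both need only a short amendment, submitted for ethics approval as Sections 4 and 10.2 require. Enrolment stays at 80 per group.
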